6.5.2 Vital signs

Vital signs include blood pressure, pulse measurements, respiratory rate, and temperature. After the patient has been supine for five minutes, systolic and diastolic blood pressure will be measured three times using an automated validated device, e.g. OMRON, with an appropriately sized cuff. The repeat supine measurements will be made at approximately 1 to 2 minute intervals and the mean of the three measurements will be used. In case the cuff sizes available are not large enough for the patient's arm circumference, a sphygmomanometer with an appropriately sized cuff may be used. After the patient has been standing for 3 minutes, systolic and diastolic blood pressure will be again measured using the above procedure.

Clinically notable vital signs for blood pressure, pulse, and weight are defined in [Appendix 1](#).

6.5.3 Height and weight

Height in centimeters (cm) and body weight (to the nearest 0.1 kilogram (kg) in indoor clothing, but without shoes) will be measured.

6.5.4 Laboratory evaluations

A central laboratory will be used for analysis of all specimens collected. Details on the collections, shipment of samples and reporting of results by the central laboratory are provided to investigators in the laboratory manual. Clinically significant abnormalities should be recorded on the Medical History/Adverse Event CRF page as appropriate.

Clinically notable laboratory findings are defined in [Appendix 1](#).

6.5.4.1 Hematology

The following parameters will be collected: standard hematology with differential (red blood cell count, white blood cell count, platelet count, hemoglobin, hematocrit, mean corpuscular volume (MCV), mean corpuscular hemoglobin (MCH), mean corpuscular hemoglobin concentration (MCHC), red blood cell morphology, white blood cell differential).

Measures of coagulability to be collected: activated partial thromboplastin time (aPTT), prothrombin time/International Normalized Ratio (PT/INR)

6.5.4.2 Clinical chemistry

The following parameters will be collected: albumin, alkaline phosphatase, amylase, bicarbonate, total bilirubin (direct and indirect bilirubin measured if total bilirubin >1.5 X ULN), calcium, chloride, cholesterol, creatinine, creatine kinase (CK), gamma-glutamyltransferase (γ -GT), glucose, lipase, lactate dehydrogenase, inorganic phosphorus, magnesium, potassium, total protein, aspartate aminotransferase (AST), alanine aminotransferase (ALT), sodium, triglycerides, urea and uric acid.

At Screening (Visit 1) the following parameters will also be analyzed to determine a patient's eligibility: HIV antibodies, hepatitis B surface antigen, hepatitis C antibodies.

Serum pregnancy will be performed in accordance with [Table 6-1](#)

6.5.4.3 Urinalysis

Dipstick measurements for specific gravity, protein, glucose and blood will be done at the site. If there are any abnormalities present, urine sample should be sent to the central laboratory for microscopy analysis.

[REDACTED]

[REDACTED]

6.5.4.5 Urine drug screen

A urine drug screen for drug abuse will include screening for cocaine, amphetamines, barbiturates, cannabinoids (including tetrahydrocannabinol), opiates, phencyclidine, and methadone.

If the results of the Screening urinalysis are positive for a prescribed medications that could be consumed abusively the site may perform a repeat urine drug screen within the screening period.

If the results from the repeat urine drug screen are negative, the patient may be included.

If the repeat results are positive, the patient must be excluded from the study and this patient cannot be re-screened in the future. A second repeat is not admissible. No repeat drug screen will be permitted for recreational drugs.

Urine drug screen will also be performed at Week 4 according to [Table 6-1](#).

6.5.5 Electrocardiogram (ECG)

ECGs must be recorded according to the ECG investigator manual. The Fridericia QT correction formula (QTcF) should be used for clinical decisions.

Single 12 lead ECGs are collected with ECG machines supplied by the core laboratory at the visits indicated in [Table 6-1](#). The original ECGs, appropriately signed, must be collected and archived at the study site.

Each ECG tracing must be labeled with study number, subject initials, subject number, date and time, and filed in the study site source documents. If the single ECG shows a QTcF > 500 ms (males or females), 2 additional ECG replicates should be recorded under continued controlled environmental conditions (patient resting, no interfering procedures to ensure as much as possible stable heart rate) to confirm the safety findings and copies forwarded to the central ECG laboratory for assessment. Shortly after completion of the triplicate ECG recording, a PK sample should be drawn to allow for correlation of PK to the QT/QTc.

If needed clinically significant ECG findings at randomization (pre-dose) may be discussed with the sponsor before administration of study treatment. Clinically significant abnormalities must be recorded on the relevant section of the Medical history/Current medical conditions/AE eCRF page as appropriate.

Detailed instructions concerning the ECG recording will be provided to all Investigators in a separate manual prior to the start of the study.

6.5.6 Pregnancy and assessments of fertility

All pre-menopausal women who are not surgically sterile will have pregnancy testing. Additional pregnancy testing might be performed if requested by local requirements.

Serum and urine pregnancy tests will be performed according to the schedule in [Table 6-1](#).

6.5.7 Appropriateness of safety measurements

The safety assessments selected are standard for this patient population. Since EMA401 is currently at Phase 2 of clinical development, safety evaluation including hematology and blood chemistry assessments are planned every 2 weeks for close patient monitoring and early detection of any safety signals.

6.6 Other assessments

6.6.1 Patient Reported Outcomes (PRO)

Please refer to [Section 6.4](#) for details on all Patient Reported Outcomes (PRO).

6.6.3 Resource utilization

Not applicable.

6.6.4 Pharmacokinetics

[figure not shown]
Further details on sample collection, numbering, processing and shipment can be found in the Laboratory Manual. The PK collection blood log is given in [Appendix 5](#).

For all patients, PK samples will be collected at Week 8 and Week 12 according to [Table 6-1](#) in order to measure EMA401 blood levels. The first blood sample should be collected after the patients have come to the clinic before taking morning study medication (i.e. EMA401/placebo). The second blood sample should be collected between 1-3 hours after the morning study

medication dose (i.e. EMA401/placebo). The third blood sample should be collected between 4-6 hours after the morning study medication dose (i.e. EMA401/placebo).

For those patients who are also taking pregabalin or gabapentin, an additional pre-dose PK sample will be collected at Baseline, Week 8, and Week 12 before the patient takes their morning dose of pregabalin or gabapentin.

PK sample should also be collected if abnormal ECG result (see [Section 6.5.5](#)).

6.6.6 Other biomarkers

Not applicable.

[figure not shown]
7 Safety monitoring

7.1 Adverse events

An adverse event (AE) is any untoward medical occurrence (e.g., any unfavorable and unintended sign [including abnormal laboratory findings], symptom or disease) in a subject or clinical investigation subject *after providing written informed consent* for participation in the study until the end of study visit. Therefore, an AE may or may not be temporally or causally associated with the use of a medicinal (investigational) product.

In addition, all reports of intentional misuse and abuse of the product are also considered an adverse event irrespective if a clinical event has occurred.

The occurrence of adverse events must be sought by non-directive questioning of the patient at each visit during the study. Adverse events also may be detected when they are volunteered by the patient during or between visits or through physical examination findings, laboratory test findings, or other assessments.

Abnormal laboratory values or test results constitute adverse events only if they fulfill at least one of the following criteria:

- they induce clinical signs or symptoms,
- they are considered clinically significant,
- they require therapy.

Clinically significant abnormal laboratory values or test results must be identified through a review of values outside of normal ranges/clinically notable ranges, significant changes from baseline or the previous visit, or values which are considered to be non-typical in patient with underlying disease. Investigators have the responsibility for managing the safety of individual patient and identifying adverse events. Alert ranges for laboratory and other test abnormalities are included in [Appendix 1](#).

Adverse events must be recorded in the Adverse Events CRF under the signs, symptoms or diagnosis associated with them, accompanied by the following information:

- the severity grade
 - mild: usually transient in nature and generally not interfering with normal activities
 - moderate: sufficiently discomforting to interfere with normal activities
 - severe: prevents normal activities
- its relationship to the study treatment
 - Yes
 - No
- its duration (start and end dates) or if the event is ongoing with an outcome of not recovered/not resolved must be reported.
- whether it constitutes a serious adverse event (SAE - See [Section 7.2](#) for definition of SAE) and which seriousness criteria have been met.
- action taken regarding investigational treatment
- its outcome (not recovered/not resolved; recovered/resolved; recovering/resolving; recovered/resolved with sequelae; fatal; or unknown)

All adverse events must be treated appropriately. Treatment may include one or more of the following:

- no action taken (e.g. further observation only)
- investigational treatment interrupted/withdrawn
- concomitant medication or non-drug therapy given
- non-drug therapy given
- patient hospitalized/patient's hospitalization prolonged (see [Section 7.2](#) for definition of SAE)

Once an adverse event is detected, it must be followed until its resolution or until it is judged to be permanent, and assessment must be made at each visit (or more frequently, if necessary) of any changes in severity, the suspected relationship to the study drug, the interventions required to treat it, and the outcome.

Information about common side effects already known about the investigational drug can be found in the Investigator's Brochure (IB). This information will be included in the patient informed consent and should be discussed with the patient during the study as needed. Any new information regarding the safety profile of the medicinal product that is identified between IB updates will be communicated as appropriate, for example, via an Investigator Notification (IN) or an Aggregate Safety Finding. New information might require an update to the informed consent and has then to be discussed with the patient.

The investigator must also instruct each patient to report any new adverse event (beyond the protocol observation period) that the patient, or the patient's personal physician, believes might reasonably be related to study treatment. This information must be recorded in the investigator's source documents; however, if the AE meets the criteria of an SAE, it must be reported to Novartis.

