3.6 Risks and benefits

The available safety information, combined with the potential of EMA401 to effectively treat neuropathic pain symptoms in patients, suggests a favorable risk-benefit ratio for exposure up to 13 weeks (see [Section 3.3](#)). Appropriate exclusion criteria are defined to ensure patient safety and allow estimation of treatment response with minimal factors that confound assessment of neuropathic pain. The risk to patients in this trial will be minimized by compliance with the

eligibility criteria and study procedures, close clinical monitoring, monitoring for treatment emergent adverse events, and discontinuation of study treatment due to adverse events or based on judgment of the investigator ([Section 5.6.2](#)). In addition, the DMC will conduct quarterly full unblinded safety reviews. The DMC will review cumulative safety data, as well as patient narratives for deaths, serious adverse events (SAEs), discontinuations due to adverse events and cases of interest (allergic dermatitis, and clinically significant abnormal hepatic and hematology values). Novartis will also report the following events to the DMC on a “real time” basis: SUSARs, Death/outcome leading to death, and cases of interest as noted above.

Study population includes patients suffering from moderate to severe pain, which is often associated with comorbid conditions (e.g. anxiety, depression and sleep disturbances). Concomitant use of medications for pain (pregabalin or gabapentin) and other comorbid diseases at stable doses is therefore allowed, no safety concerns are foreseen.

4 Population

The study population will consist of male and female patients (≥ 18 years old) with post-herpetic neuralgia (PHN). The goal is to randomize a total of approximately 360 patients in approximately 100-120 centers worldwide. Since a 40% screening failure rate is expected, approximately 600 patients will be screened.

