5.6.5 Early study termination by the sponsor

Novartis may terminate the trial for reasons related to the benefit risk assessment of treatment for participants in the study, or for regulatory or medical reasons (including slow enrollment). In the event that the study is terminated early, the Institutional Review Boards (IRBs)/Ethics Committees (ECs) will be informed and will be asked to approve the process to prematurely withdraw the participants. In general, the participant should be seen as soon as possible and assessed as a prematurely withdrawn participant from the study. The withdrawal process may include additional procedures to be followed, in order to ensure that adequate consideration is given to the protection of the participant's interests.

6 Visit schedule and assessments

[Table 6-1](#) lists all of the assessments and indicates with an "X" or "S" when the visits are performed.

Patients must be seen for all visits on the designated date or as close to it as possible. (Suggested window is +/- 3 days with the exception of V199 and V201 which must be performed no later than 13-week after the Baseline visit.)

For V199 and V201, the scheduled dates should be strictly adhered to avoid treatment exposure of more than 13 weeks after baseline visit.

The scheduled visit date should be calculated based on V101 (BL) for all visits from V101 (week 0) till V201 (week 13).

Missed or rescheduled visits should not lead to automatic discontinuation. Patients who prematurely discontinue the study treatment for any reason should be scheduled for a visit as soon as possible, at which time all of the assessments listed for the Treatment Discontinuation visit (TD) will be performed. At this visit, all dispensed investigational product should be reconciled and the adverse event and concomitant medications reconciled on the CRF. If patients then agree to continue in the study (for further safety and efficacy data collection), subsequent visits will then be according to the Abbreviated schedule of assessments for patients with study treatment discontinuation as outlined in [Table 6-2](#). Patients following the Abbreviated schedule of assessments must continue to adhere to the protocol requirements for changes to concomitant medications for neuropathic pain, rescue medication and prohibited medications.

Patients will be contacted for safety evaluations during the 30 days following the last administration of study treatment.

[figure not shown]
[figure not shown]

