⁶Should blood sampling procedures, ECG and vital signs assessments be required at the same visit, the blood sampling procedures should be started after completion of the ECG collection and hemodynamic assessments as shown in the following sequence: 10 min resting period & pre-dose single ECG → Vital signs → Pre-dose PK & lab samples → Study drug administration.

⁷Drug dispensation only for patients continuing into Treatment withdrawal epoch. Patients will take their last dose of "Treatment" study medication from their old bottle at the site visit in the morning, and will take their first dose of "Treatment withdrawal" study medication from their new bottle that evening.

⁹PK samples for all patients should be collected according to the schedule detailed in [Table 17-1](#). Patients should be instructed not to take their morning dose of study medication prior to arriving at the site and completing the necessary assessments. PK sample should also be collected if abnormal ECG result (QTcF>500 ms).

¹⁰Additional PK sample collected for patients taking pregabalin or gabapentin according to the schedule detailed in [Table 17-2](#). Patients should be instructed not to take their morning dose of pregabalin/gabapentin prior to arriving at the site and completing the necessary assessments. Patients should bring their pregabalin/gabapentin (if applicable) with them to the study visits where PK is collected so it may be administered after the PK assessment, as required.

[figure not shown]

[figure not shown]
Table 6-2 Abbreviated schedule of assessments for patients with data collected after study treatment discontinuation

Epoch	Treatment						
Visit ^{1,2}	102	103	104	105	106	107	199
Week	1	2	4	6	8	10	12
Day	8	15	29	43	57	71	85
Complete Physical exam							S
Brief Physical exam	S	S	S	S	S	S	
Surgical and medical procedures/Concomitant Medications	X	X	X	X	X	X	X
Adverse Events/SAEs	X	X	X	X	X	X	X
Complete pain diary daily (NRS)	X	X	X	X	X	X	X
BPI-SF, NPSI			X		X		X
PGIC							X
Treatment epoch disposition							X

X = assessment to be recorded on clinical data base; S = assessment to be recorded on source documentation only

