7.2.2 SAE reporting

To ensure patient safety, every SAE, regardless of causality, occurring after the patient has provided informed consent and until 30 days after the last study visit must be reported to Novartis safety within 24 hours of learning of its occurrence. Any SAEs experienced after the 30 day period after the last study visit should only be reported to Novartis safety if the investigator suspects a causal relationship to study treatment.

All follow-up information for the SAE including information on complications, progression of the initial SAE and recurrent episodes must be reported as follow-up to the original episode within 24 hours of the investigator receiving the follow-up information. An SAE occurring at a different time interval or otherwise considered completely unrelated to a previously reported one must be reported separately as a new event.

Information about all SAEs is collected and recorded on the Serious Adverse Event Report Form; all applicable sections of the form must be completed in order to provide a clinically thorough report. The investigator must assess the relationship of each SAE to study treatment, complete the SAE Report Form in English, and submit the completed form within 24 hours to Novartis. Detailed instructions regarding the submission process and requirements for signature are to be found in the investigator folder provided to each site.

Follow-up information is submitted as instructed in the investigator folder. Each re-occurrence, complication, or progression of the original event must be reported as a follow-up to that event regardless of when it occurs. The follow-up information should describe whether the event has resolved or continues, if and how it was treated, whether the blind was broken or not, and whether the patient continued or withdrew from study participation.

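### Non-serious adverse events first found at the planned 30-day post-dose safety contact need not enter the clinical database, because AE recording stops at the end-of-study visit

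*Protocol*

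**What the plan says.** Protocol Section 6 commits to contact after treatment: "Patients will be contacted for safety evaluations during the 30 days following the last administration of study treatment". Section 7.1 defines an adverse event as one arising after consent "for participation in the study until the end of study visit". That visit is V201 (Day 92) for patients who go through the withdrawal week, and V199 (Day 85) for patients who stop drug early and follow Table 6-2. Table 6-1 has nothing after V201.

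Section 7.1 also deals with new events beyond the observation period that the patient or the patient's physician suspects are drug-related: "This information must be recorded in the investigator's source documents; however, if the AE meets the criteria of an SAE", it goes to the sponsor. Events already found by the last visit are not dropped: "Once an adverse event is detected, it must be followed until its resolution or until it is judged to be permanent". Section 7.2.2 gives serious events a longer window, with every SAE "occurring after the patient has provided informed consent and until 30 days after the last study visit must be reported to Novartis safety".

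Section 9.5.2.2 names allergic dermatitis as a potential risk of EMA401, and Section 3.3.4 reports that it was more frequent on EMA401 than on placebo in the earlier PHN study. Section 3.6 has the sponsor report to the DMC in real time "SUSARs, Death/outcome leading to death, and cases of interest as noted above". The cases of interest include allergic dermatitis and carry no seriousness condition.

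SAP 2.8.1 mentions adverse events after the end of study only for the Urgent Safety Measures (USM) follow-up. Those reported 21 days past the end-of-study date are listed but kept out of the summary tables.

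**The concern.** The protocol arranges to ask patients about safety after the last dose but does not say where a new non-serious answer is entered. The treatment-emergent definition in Protocol 9.5.2.1 and SAP 2.8.1 has no end date, so the analysis would accept such events. The limit lies in data collection.

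What is at stake is the record of events that appear once drug is stopped. Section 3.3.4 gives 28 days as the longest earlier Phase 2 exposure at 100 mg b.i.d.; this trial gives 12 to 13 weeks. Section 3.2 also says the study will look for rebound in safety after the drug is stopped. A late, non-serious skin reaction is the kind of event the sponsor says it is watching for, and under Section 7.1 it may remain at the site.

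**Working it through.** **Which text governs a new non-serious event found at the contact.** Section 6 creates the contact. Section 7.1 closes the AE definition before most of the contact window, and sends later suspected-related events to source documents unless they are serious. Section 7.2.2 extends SAEs only. No other protocol text extends the window for non-serious events.

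**Inputs.** V199 is Day 85 and V201 is Day 92 (Table 6-1). Footnote 7 has patients take their last Treatment-epoch "study medication from their old bottle at the site visit in the morning" of V199, so a completer switched to placebo has the last EMA401 dose on Day 85. For a completer who continues EMA401, the last dose is assumed to fall on Day 91 or 92. Visits are taken as on schedule.

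**Formula.** Covered days = max(0, min(30, end-of-study visit day − last EMA401 dose day)). Uncovered days = 30 − covered days.

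| Group | Last EMA401 dose | End-of-study visit | Covered | Uncovered |
|---|---|---|---|---|
| Completer, EMA401 continued | Day 91–92 | Day 92 | 0–1 | 29–30 |
| Completer, switched to placebo | Day 85 | Day 92 | 92 − 85 = 7 | 23 |
| Early stopper, Table 6-2 | Day 55 | Day 85 | 85 − 55 = 30 | 0 |
| Early stopper, Table 6-2 | Day 71 | Day 85 | 85 − 71 = 14 | 16 |
| Early stopper, Table 6-2 | Day 84 | Day 85 | 85 − 84 = 1 | 29 |

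The 23 days are counted from the last EMA401 dose. Counted from the last blinded dose (placebo, Day 91–92), the switched group also has 29–30 uncovered days.

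**Are serious events affected?**
- Completers: the SAE window ends on Day 92 + 30 = 122. The contact window ends on Day 91 + 30 = 121 or 92 + 30 = 122.
- Table 6-2 patients: the SAE window ends on Day 85 + 30 = 115. The contact window ends at the latest on Day 84 + 30 = 114.

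The SAE window reaches the end of the contact window in each of these groups, so only non-serious events are left out.

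**A yardstick from the protocol.** Exclusion criterion 10a requires contraception for 3 days after stopping. Completers who continue EMA401 have 0–1 off-drug days of non-serious AE recording, which is shorter than that.

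**What cannot be computed.** The documents give no post-treatment event rate and no number of completers, so the number of missed events cannot be estimated.

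**The case against.** The strongest reply is that the rule is stated and graded, not missing. AE recording ends at the last visit, later suspected-related events go to source, and SAEs run for 30 more days. A contact meant for SAE capture and patient care fits that scheme, and no two sections contradict each other. This stands, and it is why the point is an improvement and not an error.

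Protocol 9.5.2.7 sends clinically significant findings from additional evaluations, skin assessment included, to the AE CRF with no time limit. It is the nearest counter-text. But it belongs to the analysis section, no examination is scheduled at the contact, and it does not extend the window in Section 7.1. At most it means that sites could differ in practice.

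A reader might infer that the DMC would be deprived of late dermatitis cases. The documents do not establish this. Section 7.1 requires source recording but does not forbid reporting, Section 3.6 puts no end date on real-time reporting, and the DMC charter and DMC analysis plan are not available. An event that may need medical intervention can also meet the SAE definition in Section 7.2.1 and is then covered.

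The practical reach is small as well. The trial was terminated early with 129 of 360 patients randomized, and the SAP already provides for adverse events from the USM follow-up. A protocol change can no longer alter what was collected here.

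**Conclusion.** The point holds as a low-cost improvement. Outside the USM follow-up, non-serious events first found at the planned contact need not enter the clinical database. The uncovered part of the 30 days after EMA401 is 29–30 days for completers who continue to V201, 23 for those switched to placebo, and 0 to 29 for early stoppers followed to Day 85 who stop between Day 55 and Day 84. These are calendar days without stated AE entry, not a count of lost events.

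Between-arm bias might also be inferred, but it is not shown: the cutoff is the same visit for completers in every arm. The randomized withdrawal-week comparison lies before V201 and is unaffected. No DMC decision is shown to change. The 3-day contraception requirement also suggests that late drug-related events may be few.

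The conclusion rests on on-schedule visits, a last dose on Day 91–92 for those who continue, and the protocol text alone. The eCRF instructions, which might already cover this, are not among the documents.

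**What to change.** **Protocol 7.1.** Extend AE CRF recording to the later of the end-of-study visit and 30 days after the last dose of blinded study treatment. Counting from the last blinded dose lets sites apply it without knowing the withdrawal assignment.

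**Table 6-1.** Add the contact as a footnote, or as a contact expressly stated not to be a study visit. A plain new column could be read as the last planned visit. That would move study completion (Section 5.6.1) and the end of trial (Section 3.1), and would push the SAE window to about Day 121 + 30 = 151 or 122 + 30 = 152. All three should stay tied to V201 or V199.

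**SAP 2.8.1.** List events with onset after the end-of-study visit separately. Use the treatment-sequence headers of SAP 2.1.1 for patients who entered the withdrawal epoch, and the Treatment-epoch arm for the others. Grouping by last treatment received would put events that follow 12 weeks of EMA401 under placebo. The epoch tables and the 21-day USM rule can stay.

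**Cost.** Protocol and CRF wording, one footnote and one listing. No visit, test or staff is added, since the contact is already planned. The downside is slightly more AE data entry and up to about 30 more days before the last AE data point.
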